2.1 General Methods

Any change made to the finalized SAP before database lock will result in an SAP amendment. Otherwise, changes will be documented in the Clinical Study Report (CSR). However, if additional supportive or exploratory analyses are requested after SAP approval, this will not require amendment of the SAP, but these additional analyses will be described in the CSR.

Some of the analyses detailed here may be more explicit or in some respects different from those stated in the protocol. In case of differences, this SAP supersedes the statistical sections in the protocol.

2.1.1 Programming Conventions

CCI will have responsibility for performing analyses. All computations for statistical analyses will be performed using SAS® software, Version 9.4 or later. All SAS programs used in the production of statistical summary outputs will be validated with independent programming prior to finalization. In addition, all program outputs will be independently reviewed. The validation process will be used to confirm that all data manipulations and calculations were accurately done. Once validation is complete, a senior statistical reviewer will perform a final review of the documents to ensure the accuracy and consistency with this plan and consistency within tables. Upon completion of validation and quality review procedures, all documentation will be collected and filed by the project statistician or designee.

GALDERMA EST. 1981	Title 43BBJ1911 - Statistical Analysis Plan - Big Ben Jawline
-----------------------	---

The electronic case report form (eCRF) data for all subjects will be provided in Study Data Tabulation Model (SDTM) datasets. Analysis Data Model (ADaM) datasets will be developed from the SDTM datasets for use in table and figure production.

2.1.2 Reporting Conventions

The formats for the tables, listings, and figures described in this SAP will be provided in a companion document. Changes to the formats of these reports that are decided after the finalization of the SAP will not require an amendment. In addition, any additional supportive or exploratory analyses requested after SAP approval will not require amendment of the SAP. These additional analyses will be described in the CSR.

Study data from the eCRFs as well as derived variables will be provided in subject data listings. An indication of specific listings for each data type will not be indicated in the text of subsequent SAP sections. Data listings supplied as part of the CSR will be sorted by study site number concatenated with subject number, treatment group, assessment dates, and/or time point.

The following conventions will be applied to all data presentations and analyses:

- Confidence intervals (CIs) will be two-tailed and constructed at a confidence level of 95%. Statistical tests will be performed at a significance level of 5%, and p-values will be two-sided, unless otherwise specified.
- Quantitative variables will generally be summarized by the number of subjects, mean, standard deviation, median, minimum, and maximum. Unless otherwise specified, the minimum and maximum values will be displayed to the same number of decimal places as the raw data, the mean and median will be presented to one extra decimal place compared to the raw data, and the standard deviation will be displayed to two extra decimal places compared to the raw data.
- Categorical variables will be summarized by the number and percentage of subjects (and number of events where appropriate) within each category. Unless otherwise specified, the percentage will be presented in parentheses to one decimal place. Frequency and percentage values of 0 will be presented as '0' rather than '0 (0)'.
- All summary tables will include the analysis population sample size (i.e., number of subjects) in each treatment group.
- Date variables will be formatted as DDMMYYYY for presentation.

2.1.3 Data Transformations

CCI

2.2 Analysis Populations

The statistical analyses will be performed based on the following subject populations.

2.2.1 Intent-to-Treat (ITT) Population

The ITT population includes all subjects who were randomized, and will be analyzed according to the randomization scheme. All effectiveness variables will be analyzed based on the ITT population.

2.2.2 Per-Protocol (PP) Population

The PP population includes all ITT subjects who complete the 3 months after baseline visit, and are without any deviations considered to have substantial impact on the primary effectiveness outcome. If the PP population contains less than 90% of the subjects in the ITT, a sensitivity analysis of the primary effectiveness endpoint will be performed based on the PP population. If the primary effectiveness analysis needs to be stratified (i.e., conducted separately) for the needle-treated group, the cannula-treated group, and the combination group (see SAP Section 2.4.3), then this sensitivity analysis will be performed separately for each injection tool stratum if the PP population contains less than 90% of ITT subjects within the stratum.

2.2.3 Safety Population

The Safety population includes all subjects who were treated with GP0109 or randomized to the no treatment control group, and will be analyzed according to the as-treated principle. All safety data will be summarized descriptively based on the Safety population.

2.3 Study Subjects

Demographic endpoints and subject characteristics will be summarized using descriptive statistics by treatment group and overall based on the ITT population using observed cases. There are no planned inferential statistical analyses of demographic endpoints or subject characteristics.

2.3.1 Subject Disposition

The number of subjects screened will be shown in total and by study site.

The number of subjects in each study population (i.e., ITT, PP, and Safety) will be summarized by study site and in total (by treatment group and overall).

The disposition of subjects will be presented by treatment group, and in total, including numbers of subjects who were completed and withdrawn (including primary reason for withdrawal). These numbers will also be presented by study site.

The number of subjects expected, completed, withdrawn, and missed will be summarized by scheduled visit, using the following definitions:

- Expected = all subjects at screening minus subjects who have withdrawn up to that visit.
- Completed = subjects who showed up at that visit.
- Withdrawn = all subjects who have withdrawn up to that visit (cumulative).
- Missed = expected subjects minus completed subjects.

The end of study status will be listed for all subjects (both completed and withdrawn) individually, including at least subject number, end of study date, and last visit performed. In addition, reason for withdrawal will be provided for withdrawn subjects.

2.3.2 Protocol Deviations

Subjects with any protocol deviations will be summarized by treatment group, overall, by site, and by type. Subjects with out-of-window visit protocol deviations will be presented by visit and number of days out of window for each treatment group and overall.

Depending on the seriousness of a protocol deviation, a subject might be excluded from the PP population, which shall be documented prior to database lock. Since the PP population will be used for the primary analysis at 3 months after baseline only, the focus will be on major deviations occurring before and at the Month 3 visit which are considered to have a substantial impact on the primary effectiveness outcome, see Table 3 below for list. Reasons for exclusion from the PP population also will be summarized.

Table 3. Major Protocol Deviations Causing Exclusion from Per-Protocol Population

Major Deviation
Month 3 visit out of window by greater than 21 days or earlier than 7 days
Subject did not receive treatment as randomized
Galderma Jawline Scale live assessment by Blinded Evaluator not done on at least one side of face at Month 3 (primary endpoint)
Galderma Jawline Scale live assessment by Blinded Evaluator not done on at least one side of face at screening or baseline
Galderma Jawline Scale live assessment by Blinded Evaluator at baseline is not grade 2 to 4 (moderate to very severe) on at least one side of face
More than one grade difference in Galderma Jawline Scale between left and right side of face at baseline as assessed live by Blinded Evaluator
Prohibited concomitant treatments/procedures prior to Month 3 visit considered to have substantial impact on primary effectiveness outcome
Prohibited medical history, unstable medical history condition, or medical history condition that worsens prior to Month 3 visit considered to have substantial impact on primary effectiveness outcome

2.3.3 Demographic Characteristics

Age and body mass index will be summarized as continuous variables.

Gender, race, ethnicity, FST, childbearing potential, and baseline GJS (Blinded Evaluator and Treating Investigator) will be summarized as categorical variables.

2.3.4 Medical History, Medications, and Procedures

Prior and concomitant medications and vaccines will be coded using the World Health Organization Drug Dictionary (WHODD). Medical history, prior cosmetic treatments/procedures, procedural anesthetics, and concomitant procedures/treatments will be coded according to the Medical Dictionary for Regulatory Activities (MedDRA).

Prior medications/procedures are the medications/procedures with stop dates prior to first study treatment session for the GP0109 treatment group and prior to randomization for the no treatment control group. Medications/procedures after the first study treatment session or randomization will be considered concomitant.

Subjects reporting medical history, prior cosmetic treatments/procedures, and concomitant procedures/treatments will be summarized by System Organ Class (SOC) and Preferred Term (PT). Procedural anesthetics will only be listed.

Subjects reporting concomitant medications and vaccines will be summarized separately, by WHODD Anatomical Therapeutic Chemical (ATC) Class Level 3 (if Level 3 is not available, the highest class available will be used) and WHODD preferred name. Prior medications will only be listed.

2.4 Effectiveness Analysis

2.4.1 Datasets Analyzed

The ITT population is primary for all effectiveness analyses. The primary effectiveness analysis will be repeated using the PP analysis population if there is at least a 10% difference in the number of subjects between the PP and ITT populations. If the primary effectiveness analysis needs to be stratified (i.e., conducted separately) for the needle-treated group, the cannula-treated group, and the combination group (see SAP Section 2.4.3), then this analysis will be repeated separately for each injection tool stratum if the PP population contains less than 90% of ITT subjects within the stratum.

2.4.2 Handling of Missing Data

Number of missing values will be summarized and reported as appropriate.

For the ITT analysis of the Blinded Evaluator GJS responder rates and CCI [REDACTED] at 3 months after baseline (primary and first secondary endpoint), missing values will be assumed to be missing due to lack of effect. Therefore, the primary method of imputation will use the baseline observation carried forward (BOCF) method. Impact of missing data on the primary and first secondary endpoint will be evaluated by performing sensitivity analysis based on the observed cases in the ITT set.

CCI [REDACTED]

All other effectiveness endpoints will be evaluated based on the observed cases in ITT.

2.4.3 Primary Effectiveness Analysis

Responder rate based on the GJS, as assessed live by the Blinded Evaluator at 3 months after baseline, will be the primary effectiveness endpoint. A responder will be defined as a subject with at least 1 grade improvement from baseline on both sides of the face concurrently.

The null hypothesis will be that there is no relationship between responder rate and treatment group (i.e., the responder rate is the same in treated and untreated subjects). The alternative hypothesis will be that there is a relationship between responder rate and treatment group (i.e., the responder rate is different in treated subjects compared to untreated subjects).

[figure not shown]
The estimates of the responder rate in each treatment group will be presented as well as the difference in responder rates. Corresponding confidence intervals for responder rates (via Clopper-Pearson) and the difference in responder rates (via normal approximation) along with the p-value (via Fisher's exact test) for the difference will also be presented.

First, the Breslow-Day test for homogeneity of odds ratios will be used to assess consistency of GJS odds ratios across all injection tool strata (the needle-treated group, the cannula-treated group,

[figure not shown]

and the combination group). A significance level of 0.05 will be used to determine if the responder rates are non-homogenous. If the Breslow-Day p-value is less than or equal to 0.05, the primary analysis will be stratified (i.e., conducted separately) for the needle-treated group, the cannula-treated group, and the combination group, using a significance level of 1.7% to account for multiplicity. If the Breslow-Day p-value is greater than 0.05, the analysis will be carried out on pooled groups, using a significance level of 5%. Regardless of whether the primary analysis will be based on pooled injection tool groups, or done separately, the no treatment control group subjects will be pooled across all study sites. In either case, the primary analysis will be repeated in each injection tool stratum as part of the pre-planned subgroup analyses (see SAP Section 2.4.5).

In order to assess the poolability of study sites, a Breslow-Day test for homogeneity of odds ratios across sites will be performed. Regardless of results, the primary analysis will be repeated for each study site as part of the pre-planned subgroup analyses (see SAP Section 2.4.5).

GALDERMA <small>EST. 1981</small>	Title 43BBJ1911 - Statistical Analysis Plan - Big Ben Jawline
--------------------------------------	--

- 

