4.2 Number of subjects

Approximately 224 subjects will be enrolled at approximately 15 sites in the US. At least 45 subjects will be Fitzpatrick Skin Type (FST) IV through VI. This includes at least 23 subjects with FST V-VI, where at least 12 subjects will be FST V and at least 11 will be FST VI.

	
CCI
 

 

 
Title CTN 43BBJ1911 US Jawline, Clinical Investigation Plan

---	--

Stage 1 includes the first approximately 50 eligible subjects that will be randomized to treatment or to no treatment. At least 10 of these subjects will be FST IV-VI, with at least 3 subjects with FST V and at least 2 subjects with FST VI.

The duration of the enrollment period for Stage 2 is expected to be 4 months. Approximately 15 subjects will be included and treated at each site. The aim is to achieve an even distribution of subjects between the assigned sites.

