2.4.5 Subgroup Analyses

In order to investigate the homogeneity of the results of the analyses of the primary endpoint, as well as the first secondary endpoint, across different subgroups, the following factors will be used for definition of subgroups: injection tool (needle, cannula, and combination), study site, FST (I-III and IV-VI), race, ethnicity, gender, age group (\leq median age and $>$ median age), and total injection volume group (\leq median total injection volume and $>$ median total injection volume). Pooling of subgroup categories may be needed based on observed data. The no treatment control group subjects will be pooled across all study sites for the injection tool and injection volume subgroup analyses.

For the primary endpoint, Fisher’s exact tests will be used for comparison of responder rates, as well as confidence intervals of the differences in responder rates within each subgroup. These will be displayed in graphs.

If the primary effectiveness analysis is stratified by injection tool, the subgroup tables will also be stratified, although interpretation should be cautious given sample sizes may be small.

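### By-site 95% intervals for the difference in responder rates use a normal approximation that covers only about 80-85% at roughly 11 treated and 4 control subjects per site

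*SAP*

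**What the plan says.** SAP 2.4.3 specifies the intervals for the primary endpoint: "Corresponding confidence intervals for responder rates (via Clopper-Pearson) and the difference in responder rates (via normal approximation", with a Fisher exact p-value beside them. It also says that, whatever the Breslow-Day result across sites, "the primary analysis will be repeated for each study site as part of the pre-planned subgroup analyses". The same section repeats the analysis in each injection-tool stratum.

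SAP 2.4.5 covers the subgroups: tool, site, Fitzpatrick skin type (FST), race, ethnicity, gender, age and injection volume. It plans Fisher tests "as well as confidence intervals of the differences in responder rates within each subgroup", and adds "These will be displayed in graphs". It names no interval method of its own.

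Two further provisions in SAP 2.4.5 matter:
- "The no treatment control group subjects will be pooled across all study sites for the injection tool and injection volume subgroup analyses". A site is therefore compared with its own controls.
- "Pooling of subgroup categories may be needed based on observed data". No minimum size or merging rule is given.

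SAP 2.1.2 sets all intervals at 95%, two-sided. On site size, Protocol 4.2 says: "Approximately 15 subjects will be included and treated at each site".

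**The concern.** The plain normal-approximation (Wald) interval for a difference in proportions needs reasonable numbers in both arms. With about four controls it is unreliable. If none or all of them respond, the control arm's estimated variance is zero and the interval reflects the treated arm alone. The interval is also centred on the raw difference, and its limits can pass ±100%.

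At stake is how the by-site graph is read. A reader will take each bar as a 95% interval. If the true figure is nearer 80%, roughly one bar in five misses the true difference instead of one in twenty, and sites may look different from each other when they are not.

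**Working it through.** **Inputs**
- 224 subjects, 3:1, about 15 sites (SAP 1.1.2). 224/15 = 14.9 per site, of whom 14.9 × 3/4 = 11.2 are treated and 3.7 are controls. I use 11:4.
- FST IV-VI: at least 45 subjects (SAP 1.1.2). 45 × 3/4 = 33.75, so about 34:11.
- Responder rates of 70% and 32% (SAP 2.7.3).
- 10% dropout at Month 3 (SAP 2.7.4), with missing values set to baseline and so to non-response (SAP 2.4.2): 0.9 × 70% = 63% and 0.9 × 32% = 28.8%. Equal dropout in both arms is my assumption.

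**The plan's own figures.** Exact Fisher power for 70% against 32% is 99.7% at 150:50 and the 5% level (stated: more than 99%), and 91.8% at 50:50 and the 1.7% level (stated: about 90%). 200/0.9 = 222.2, rounded up to 223, against 224 stated. The inputs agree with the plan.

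**Method.** The interval is p1 − p2 ± 1.96 × √[p1(1 − p1)/n1 + p2(1 − p2)/n2], with observed proportions and no continuity correction. Coverage is the total binomial probability of all outcome pairs whose interval contains the true difference. It is an exact sum, not a simulation.

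| Comparison | Rates | Wald | Wald, continuity-corrected | Newcombe | Miettinen-Nurminen |
|---|---|---|---|---|---|
| Site 11:4 | 70/32% | 84.8% | 92.1% | 96.0% | 96.1% |
| Site 11:4 | 63/28.8% | 80.4% | 94.6% | 94.7% | 96.4% |
| Site 12:4 | 70/32% | 81.0% | 93.2% | 95.1% | 96.0% |
| Site 11:3 | 70/32% | 78.4% | 93.2% | 95.3% | 95.5% |
| Site 11:3 | 63/28.8% | 74.2% | 91.6% | 93.7% | 96.9% |
| Site 12:3 | 70/32% | 73.2% | 88.7% | 94.6% | 96.2% |
| FST IV-VI 34:11 | 70/32% | 90.9% | 95.5% | 94.6% | 94.9% |
| One tool, 56:56 | 70/32% | 94.4% | 95.8% | 94.5% | 94.8% |
| Primary, 168:56 | 70/32% | 94.4% | 96.2% | 94.9% | 95.0% |

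**Why coverage falls**
- Four controls with none or all responding: 0.32⁴ + 0.68⁴ = 22.4%; at 28.8%, 0.288⁴ + 0.712⁴ = 26.4%. Example, 8/11 against 0/4: the difference is 72.7% and the standard error is √(0.727 × 0.273/11) = 0.134, so Wald gives 46% to 99%. Newcombe gives 16% to 90%.
- Centring: at 11:4 and 70/32%, 12.2% of Wald intervals lie wholly above the true difference and 3.0% wholly below it.
- Limits beyond ±100%: 18.9% of sites at 70/32% and 10.9% at 63/28.8%. Example, 9/11 against 1/4: the difference is 56.8% and the standard error is √(0.0135 + 0.0469) = 0.246, so Wald gives 9% to 105%. Newcombe gives 3% to 81%.

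**Width.** At 11:4 and 70/32%, the mean width is 0.916 for Wald and 0.806 for Newcombe. Newcombe is wider than Wald cut at ±100% in only 23% of outcomes, about the share with a degenerate control arm. At 34:11 the means are 0.603 and 0.552.

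**Agreement with Fisher.** At 11:4, the chance that Wald excludes zero while Fisher p > 0.05 is 18.5% (70/32%) and 21.7% (63/28.8%), or 2.8 to 3.3 of 15 sites. Either score interval gives 13.3% and 11.4%, or 2.0 to 1.7 sites. In the 9/11 against 1/4 example, Fisher p = 0.077 and both Wald and Newcombe exclude zero.

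**The case against.** - **The method is not named in SAP 2.4.5.** True. Carry-over is explicit for site and tool, because 2.4.3 repeats the primary analysis there. For FST, race, ethnicity, gender, age and volume it is an inference, so the 91% for FST IV-VI is conditional.
- **A normal approximation may include a continuity correction.** It may, and coverage at 11:4 would then be 92-95%. The SAP does not mention one.
- **Small categories may be pooled.** That is allowed, but with no size rule it does not settle which sites are plotted alone.
- **Site consistency is already tested.** This stands. SAP 2.4.3 plans Breslow-Day tests across sites and across tools, so a reader who infers that the graphs are the plan's only evidence of consistency goes too far.
- **The bars are not simply too short.** This also stands. Wald bars at 11:4 are on average wider than Newcombe bars; the fault is degenerate control arms and poor centring.
- **Disagreement with Fisher would remain.** Yes. Much of it comes from Fisher's conservatism at these sizes, and a score interval reduces it without removing it.

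A reader might also object to low power within subgroups: 16.7% for one site and 56.8% for FST IV-VI at the planned rates. The documents do not support treating this as a defect. SAP 2.7.4 powers only the pooled and by-tool tests, and no decision rests on a subgroup p-value.

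**Conclusion.** The concern holds for the by-site intervals. At about 11:4 and the planned rates, an uncorrected nominal 95% interval covers about 80-85%, and about 73-78% at sites with 11 or 12 treated subjects and 3 controls. For FST IV-VI the shortfall is smaller (about 91%) and depends on the same method being used there.

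This assumes no continuity correction, no merging of sites, and site sizes near the average. Site counts will vary, since only FST I-III is stratified by site.

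It would be wrong to infer that the primary result is in doubt. Coverage is 94.4% at 168:56 and 94.4-95.0% at 56:56 over the two pairs of rates, and the primary p-value is Fisher's. The point is worth correcting because it affects how the site display is read, not whether the trial succeeds.

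**What to change.** In SAP 2.4.3 and 2.4.5, replace the normal approximation with a Miettinen-Nurminen or Newcombe score interval for the risk difference, at least for the subgroup displays, and name it in 2.4.5 so that no carry-over has to be inferred. At the planned rates, coverage becomes about 95-96% at 11:4 and about 95% at 34:11.

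The cost is one SAS RISKDIFF option and a sentence, made as an SAP amendment before database lock. Design, sample size and primary test do not change. Intervals become wider where the control arm is degenerate and often shorter elsewhere. A note under the graphs should say that an interval and its Fisher p-value can still disagree, in about 11-13% of sites of this size.

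An optional addition is a treatment-by-subgroup interaction estimate for FST, race, ethnicity, gender and age, where the readable text plans no heterogeneity test. Site and tool already have Breslow-Day.

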2.7.3 Assumptions

Based on results in clinical studies of injectable fillers in the facial areas, it is reasonable to assume a responder rate of at least 70% in the GP0109 treatment group at 3 months after baseline. For the no treatment control group, responder rates up to almost 30% have been observed in the data on file. Based on this, it is assumed that the response rate will be maximum 32% in the no treatment control group at 3 months after baseline.

CCI

GALDERMA <small>EST. 1981</small>	Title 43BBJ1911 - Statistical Analysis Plan - Big Ben Jawline
--------------------------------------	---

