2.7.4 Calculations

A two-sided test at the 5% significance level will have more than 99% power to demonstrate a difference between a responder rate of 70% in the GP0109 group and a responder rate of 32% in the no treatment control group when the sample sizes are 150 and 50, respectively.

Performing the same test, but in needle, cannula, and combination subjects separately (at the 1.7% level of significance for each test to account for multiplicity), the power will be approximately 90% (assuming the same responder rate of 70% in all GP0109 groups (needle, cannula, and combination). All no treatment control group subjects will be included in each of the by strata tests.

Accounting for approximately 10% dropouts at 3 months after baseline, approximately 224 subjects need to be randomized in a 3:1 ratio (GP0109 to no treatment control group).

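### The visible primary test ignores the Blinded Evaluator's baseline GJS grade; stratifying by it would be a cheap but modest gain in precision and robustness

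*SAP*

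**What the plan says.** SAP 2.4.3 defines a responder by "at least 1 grade improvement from baseline on both sides of the face concurrently". It presents "the difference in responder rates (via normal approximation) along with the p-value", with the p-value from Fisher's exact test. The only stratification in the visible primary analysis is conditional: if a Breslow-Day test across injection tools gives p ≤ 0.05, each tool is tested separately at 1.7%. Otherwise all treated subjects are pooled and tested at 5%. Controls are pooled across all sites in both cases.

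The Blinded Evaluator grades the GJS at screening and, if that is a separate visit, again at baseline (schedule of events). The grade determines eligibility (grade 2 to 4, protocol 5.2) and is the reference for responder status. Beyond that, SAP 2.3.3 says that "baseline GJS (Blinded Evaluator and Treating Investigator) will be summarized as categorical variables". It is not a randomization stratum (SAP 1.1.2: tool, Fitzpatrick group, and site within types I-III) and not a listed subgroup factor (SAP 2.4.5).

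On power, SAP 2.7.4 says "A two-sided test at the 5% significance level will have more than 99% power" for the pooled comparison. For the by-tool tests, "at the 1.7% level of significance for each test to account for multiplicity", it says "the power will be approximately 90" percent. SAP 2.7.3 assumes "a responder rate of at least 70% in the GP0109 treatment group at 3 months after baseline" and at most 32% in controls.

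**The concern.** The endpoint is a one-grade change on a bounded 0-4 scale, and subjects start at 2, 3 or 4. The scale's description of grade 4 (SAP Table 1) adds excess skin to the volume deficit, and the product works by adding volume. The chance of gaining a grade on both sides may therefore depend on the starting grade. Measuring change from a subject's own baseline does not remove that dependence.

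If grade is prognostic, stratifying by it narrows the interval and corrects the estimate for chance imbalance against about 56 controls.

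In the by-tool comparisons the imbalance need not be chance. Each site is assigned one tool in advance, yet every by-tool test uses all controls. With controls spread evenly over three tools, about two-thirds of them come from sites using a different tool and were not randomized against the treated subjects in that test. A different grade mix between site groups would then bias the difference systematically. SAP 2.4.3 runs by-tool comparisons as subgroup analyses whatever the Breslow-Day result, so this is not confined to the fallback.

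**Working it through.** **Inputs from the documents:** 70% v 32% responders; 150 v 50 evaluable; 224 randomized 3:1 (168 v 56, about 56 treated per tool); two-sided 5% pooled, 1.7% by tool; 10% dropout; missing values filled by baseline carried forward (SAP 2.4.2), which makes them non-responders.

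**Assumed, because SAP 2.7.2 says there are no data on the new scale:** baseline grades 2/3/4 in 50/35/15% of subjects; one grade per subject; the same OR per grade in both arms.

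**1. The plan's own figures (exact Fisher power, enumerating both binomials).**
- Pooled, 150 v 50 at 5%: 99.7% (stated: more than 99%).
- By tool, 50 v 50 at 1.7%: 91.8% (stated: about 90%).
- Dropout: 200/0.9 = 222.2, so 223 (stated: 224).

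These reproduce.

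**2. The same tests as the ITT analysis will run them.** Counting 10% missing as non-responders gives 0.9 × 70% = 63% and 0.9 × 32% = 28.8%.
- Pooled Fisher, 168 v 56 at 5%: 99.4%.
- By-tool Fisher, 56 v 56 at 1.7%: 87.3%, with a true size of about 1.0% against the allowed 1.7%.
- By-tool unadjusted chi-square: 90.9%. Check by normal approximation: mean rate (63 + 28.8)/2 = 45.9%; null SE = √(0.459 × 0.541 × 2/56) = 0.0942; alternative SE = √(0.63 × 0.37/56 + 0.288 × 0.712/56) = 0.0885; power = Φ[(0.342 − 2.387 × 0.0942)/0.0885] = Φ(1.32) ≈ 91%.

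**3. CMH stratified by grade, by-tool branch (simulation, grades 2, 3 and 4 kept separate).**

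| OR per grade | Fisher | Unadjusted chi-square | CMH by grade | CMH minus chi-square |
|---|---|---|---|---|
| 1 | 87.3% | 90.9% | about 90% | about -1 point |
| 1.5 | 87.3% | 90.9% | about 91% | about 0 |
| 2 | 87.3% | 90.9% | about 92% | about +1 |
| 3 | 87.3% | 90.9% | about 94% | about +3 |

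Leaving Fisher alone gives 90.9 − 87.3 = 3.6 points. Using grade adds −1 to +3 points on top. Merging grades 3 and 4, as the fix proposes, changes these figures only slightly.

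**4. Precision.** In the by-tool branch at OR 3 the SD of the difference falls from 0.0882 to 0.0841, and 1 − 0.0841/0.0882 = 4.6%. In the pooled analysis the reduction is about 2% at OR 2 and 4-5% at OR 3. If grade is not prognostic, the SD is about 1% larger.

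**5. Chance imbalance, pooled.** If half the subjects are grade 3-4, the SD of the between-arm difference in that share is √[0.25 × (1/168 + 1/56)] = 7.7 points. At OR 2 this contributes about 1.6 points of SD to the responder difference. The total SE is √(0.63 × 0.37/168 + 0.288 × 0.712/56) = 7.1 points, and that already includes it.

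**6. Systematic imbalance, by tool (illustration).** Suppose no treatment effect, OR 2 per grade, and response rates of 19.7%, 32.9% and 49.5% at grades 2, 3 and 4. Let one tool's sites have a 65/25/10% mix and the other two tools' sites 42.5/40/17.5%, so that all controls together have 50/35/15%.
- Pooled controls: 0.50 × 19.7 + 0.35 × 32.9 + 0.15 × 49.5 = 28.8%.
- Treated at that tool: 0.65 × 19.7 + 0.25 × 32.9 + 0.10 × 49.5 = 26.0%.

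The raw difference is off by 2.8 points with no treatment effect. Comparison within grade removes it, because the rates within each grade are equal by construction.

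**The case against.** The strongest reply is that the planned test is valid, pre-specified and, for the pooled comparison, already powered above 99%. All of that stands. A reader might infer that chance imbalance in grade inflates the false-positive rate. It does not: the exact size of the pooled Fisher test at a common 32% rate is 4.0%, and simulation kept it at about 4% at every prognostic strength tried. A reader might also infer that the plan gives up material power. At the planned effect, the pooled loss is at most 0.3 points.

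The by-tool branch is a fallback, entered nominally about 5% of the time if the tools have equal odds ratios. Most of the apparent gain there belongs to dropping Fisher's test. The benefit from grade also depends on an unknown prognostic strength and on similar slopes in both arms. With OR 2 in treated subjects and 1 in controls, CMH power is 90.1%; with 2 and 0.5 it is 89.7%. Both are below the unadjusted chi-square. These limits stand too.

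Finally, it is tempting to say that the plan does nothing with baseline grade except tabulate it. The documents do not support that. The grade also sets eligibility and responder status, and SAP 2.4.4 and part of 2.4.2 are redacted, so an adjusted supportive analysis cannot be ruled out.

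What the reply does not remove is the possible precision gain and the exposure of by-tool comparisons to controls from other sites.

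**Conclusion.** The point holds as a low-cost improvement, with moderate confidence. It is not an error that threatens the primary conclusion. The visible primary analysis leaves out a baseline value that is already collected and plausibly prognostic. For the pooled test the benefit is an SD about 2% smaller at OR 2 and 4-5% smaller at OR 3, with no meaningful change in power. In the by-tool branch, CMH by grade reaches about 90-94% against 87.3% for Fisher, but only −1 to +3 points of that come from grade.

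The power gain would matter more if the true effect were well below plan. At an assumed 52% v 32%, pooled 150 v 50, power is 68% for Fisher, 71% for chi-square and 69-80% for CMH over ORs of 1 to 4.5 per grade.

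All of these gains rest on the assumed grade mix and ORs. The argument about borrowed controls rests on the documents for the design, and on assumption for whether grade mix differs between site groups.

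**What to change.** In SAP 2.4.3, for both the pooled and by-tool branches:

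- Make the primary test a CMH test stratified by the Blinded Evaluator's baseline GJS on the worse side, grade 2 v 3-4. Fix this split in advance rather than merging grades according to the data.
- Combine it with the randomization strata where feasible. Tool can be added in the pooled branch. It cannot be a stratum within a by-tool test that uses all controls, because controls from the other tools' sites would have no treated counterparts.
- Report the Mantel-Haenszel or a standardized risk difference with its confidence interval.
- Keep the unadjusted Fisher test as a sensitivity analysis.

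The change has to be made before the data are seen; adjusting after an imbalance is noticed would carry little weight. If the redacted SAP 2.4.4 already holds such an analysis, a cross-reference and a decision on which analysis is primary would be enough.

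The cost is SAP wording and a few lines of SAS, with no new data. The downsides are an SD about 1% larger and power about 1 point below an unadjusted chi-square if grade is not prognostic. An asymptotic test also replaces an exact one; its simulated size in the by-tool branch was 1.6-1.8% at the nominal 1.7%. The worse side is one of several defensible summaries of a two-sided baseline.
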